#### 16.0 Data Analysis

- **16.1** In all cases, the blood analysis data are provided, including the SaO2, MetHb, COHb and Hgb concentration.
- **16.2** The data analysis report will consist of the following:
  - **16.2.1** A Table of the oximeter readings versus corresponding blood SaO2 values.
  - **16.2.2** Graphic plots of the bias between the oximeter reading and the SaO2 measured by the hemoximeter (on the blood sample, i.e Modified Bland-Altman plots for each instrument or instrument probe combination).
  - **16.2.3** Regression equations for the bias of each instrument.
  - **16.2.4** Tables of the mean error or bias, its standard deviation, standard error, 95% confidence interval, maximum and minimum and root mean square error, all computed both overall and by several sub-ranges of desaturation.
  - **16.2.5** A table of the demographics of the subject population is provided.

# 17.0 Subject Safety

**17.1** Pulse oximeter sensors are typically considered non-significant risk medical devices. The LED light energy utilized in typical test measurements is within the same range as other cleared marketed devices and introduces no further risks. An LED light emits light that passes through the

DF-CDS-109-11	UNCONTROLLED WHEN PRINTED
Rev. L	STRYKER CONFIDENTIAL - This document contains confidential and proprietary
Sustainability Document Template	information that is the property of Stryker Corporation. Neither this document nor the information herein may be reproduced, used or disclosed to any third party without the prior written consent of Stryker Corporation.

Document No:	CRD10351
Revision:	Α
Page:	9 of 11

tissue. A light detector then measures how much light was absorbed by the tissue. Based on the ratio of absorbance of different wavelengths of light, the device calculates the oxygen saturation.

#### 18.0 Risks and Benefits of the Investigational Device and Clinical Investigation

- 18.1 Breathing a very low oxygen mixture may cause dizziness and might cause loss of consciousness for a few seconds. It may make one feel very short of breath during the test and for a few seconds afterwards. There is a remote possibility that if the subject loses consciousness, he/she might have muscular twitching or convulsions. This study will not seek to reach saturations below 70%. Hypoxia may cause tachycardia and increased blood pressure during the test and might cause headache. In all the years of the lab conducting the study no subject has mentioned headache. Much more severe and prolonged lack of oxygen could cause brain injury or death, but the duration and depth of hypoxia is limited by the test protocol to short intervals. The needle catheter used to take blood may hurt when it is inserted despite the use of local anesthesia, and there may be a black and blue spot afterward. It is remotely possible the artery might be damaged or clot, or a tendon sheath near it be injured by the needle, resulting in some soreness. These risks are unlikely because none of the enrolled 2000+ subjects has ever had a serious complication. Hyperventilating during the part of the study requiring reduced PCO2 may make subjects lightheaded or dizzy. Breathing air with added CO2 may make subjects feel short of breath and cause a headache. Some subjects feel faint when they arrive for the study, apparently related to the thought of having an arterial line. These subjects will likely be excluded from the study.
- 18.2 Currently the FDA defines pulse oximeters as Class II devices which transmit radiation at a known wavelength(s) through blood and to measure the blood oxygen saturation based on the amount of reflected or scattered radiation and may be used alone or in conjunction with a fiberoptic oximeter catheter. All oximeters being used in this study work by transmittance of radiation at known wavelength(s) through tissue to measure blood oxygen saturation based on the amount of reflected and scattered radiation. The devices under test and this study procedure are considered Non-Significant Risk (NSR).

Non-significant risk letter and checklist were sent to test lab and accepted per a previously approved UCSF IRB for an identical test which can be obtained from UCSF with reference number 330726.

The device and use of the device under test does not meet the definition of a significant risk device. Under 21 CFR 812.3(m), an SR device means an investigational device that:

- Is intended as an implant and presents a potential for serious risk to the health, safety, or welfare of a subject;
- Is purported or represented to be for use supporting or sustaining human life and presents a
  potential for serious risk to the health, safety, or welfare of a subject;
- Is for a use of substantial importance in diagnosing, curing, mitigating, or treating disease, or
  otherwise preventing impairment of human health and presents a potential for serious risk to
  the health, safety, or welfare of a subject; or
- Otherwise presents a potential for serious risk to the health, safety, or welfare of a subject.

#### 19.0 Invasive Laboratory Testing on Healthy Volunteers

19.1 The risk determination is based on the use of the device in an investigation in addition to the device itself. Generally, the FDA believes pulse oximeters as addressed in the FDA Guidance Document for Pulse Oximeters (March 4, 2013) are non-significant risk devices. Further, the recommendation is to conduct the study in accordance with Clause 201.12.1.101.2 and Annex EE.2 of ISO 80601-2-61:2019, where Annex EE.2 describes the procedure for invasive laboratory testing on healthy volunteers.

DF-CDS-109-11	UNCONTROLLED WHEN PRINTED		
Rev. L	STRYKER CONFIDENTIAL - This document contains confidential and proprietary		
Sustainability Document Template	information that is the property of Stryker Corporation. Neither this document nor the information herein may be reproduced, used or disclosed to any third party without the prior written consent of Stryker Corporation.		

Document No:	CRD10351	
Revision:	Α	
Page:	10 of 11	

#### 20.0 Risk Mitigations

Subjects are all monitored with accurate reference oximeters and continuous end-tidal gas analysis to prevent the risk of more profound hypoxia than desired. Investigators are experienced anesthesiologists adept at assessing breathing and in maintaining appropriate airway conditions. The study room is set up like an OR with all resuscitation equipment immediately available.

#### 21.0 Informed Consent

- 21.1 Written informed consent is obtained before any study interventions. In discussions with the study coordinator before the day of the study, potential subjects will be offered the consent form to review. On the day of the study subjects are given the consent form which they read and sign if they wish to participate. A study doctor is present to answer questions.
- **21.2** Only subjects clearly able to understand and read English will be enrolled. Subjects will be asked if they have any questions and are told they can withdraw at any time.

#### 22.0 Investigational Review Board (IRB)/Independent Ethics Committee (IEC)

- **22.1** Prior to the start of subject enrollment, the investigator will be responsible for obtaining approval from the authorized IRB/IEC for the institution at which the proposed clinical investigation is to be conducted. Written approval from the IRB/IEC should specifically refer to the investigator, the protocol title and date, and subject informed consent date.
- **22.2** Written IRB/IEC approval and any conditions of approval imposed by the IRB/IEC was obtained by the sponsor/investigator.
- **22.3** Protocol amendments must also undergo IRB/IEC review and approval at each clinical site. The written approval from the IRB/IEC for the amendment should specifically refer to the investigator, the protocol version number and title, and any amendment numbers that are applicable.
- **22.4** The IRB approval for this study was obtained May 16th 2023 and is valid through December 19th 2023. Approval reference number 375731.

#### 23.0 Monitoring Arrangements

- **23.1** A representative from the sponsor and study monitor will provide all monitoring. The Monitor shall be responsible for maintaining a record of the findings, conclusions, and actions taken for the results of monitoring the study ensuring that:
- 23.2 The monitoring requirements for an NSR device study is identified in 21 CFR 812.2(b) Abbreviated requirements. For monitoring an NSR device investigation, the requirement is to comply with 21 CFR 812.46 with respect to monitoring investigations: (a) Securing Compliance, (b) Unanticipated adverse device effects, (c) Resumption of terminated studies
  - Compliance to the signed agreement between the Investigator and sponsor
  - The study follows the protocol and any amendments that apply
  - Compliance to any conditions of the approval imposed by the IRB or FDA
- **23.3** Sponsor will assess any new hazards/harms identified during a clinical investigation (i.e., pre- or post-market study) as part of the risk management process per DPCDS-013, Risk Management and the complaint handling process per DP-MCF-001, Division Complaint Handling Process, as applicable.

#### 24.0 Data Storage

24.1 Identifiable subject information is always stored securely following all applicable rules and regulations. Consent forms and other study related documents are retained following UCSF data retentions policy.

DF-CDS-109-11	UNCONTROLLED WHEN PRINTED
Rev. L	STRYKER CONFIDENTIAL – This document contains confidential and proprietary
Sustainability Document Template	information that is the property of Stryker Corporation. Neither this document nor the information herein may be reproduced, used or disclosed to any third party without the prior written consent of Stryker Corporation.

Document No:	CRD10351	
Revision:	Α	
Page:	11 of 11	

#### 25.0 Acceptance Criteria

- 25.1 The statistical results of the data will be reviewed for the following pass/fail criteria:
  - **25.1.1** At least 200 data points with SpO2 Accuracy for the range of 70-100%, 3% (ARMS) is considered a Pass per FDA guidance.
  - **25.1.2** At least 10 participants where at least two participants or 15% of participant population will have dark skin pigmentation per the Fitzpatrick scale.

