#### **General Information**

#### 1.0 Purpose

1.1 The purpose of this clinical study is to validate the SpO2 accuracy of the Stryker Sustainability Solutions pulse oximetry sensors during motion conditions over the range of 70-100% SaO2 as compared to arterial blood samples assessed by CO-Oximetry during conditions in which the subject is moving. The end goal is to provide supporting documentation for the SpO2 accuracy validation of the reprocessed sensors with motion indications.

In this study, the level of oxygen within the blood will be reduced in a controlled manner by reducing the concentration of oxygen the study volunteer breathes. The accuracy of a noninvasive pulse oximeter sensor will be assessed by comparison to the oxygen saturation measurements from a laboratory blood gas analyzer.

A machine will be used to induce motions of 20 mm during testing at a sine rate of 2Hz, 3Hz, and 4Hz. A third motion moves the arm a random distance of 0 to 30mm at a random speed up to 5Hz.

It is required that the Accuracy Root Mean Square (ARMS) performance of the Stryker pulse oximetry sensors will meet a specification of +/-3% with a target of +/-3% or better in motion conditions for the range of 70 - 100% SaO2 (typically, saturation is determined once with air breathing and then at three or six levels, e.g. 94%, 90%, 85%, 80%, 75% and 70% or 95%, 85% and 75% saturation for about 30-60 seconds or 60-90 seconds at each level), thereby demonstrating an acceptable SpO2 accuracy performance specification. This study should utilize a three level structure (95%, 85% and 75%).

**1.2** This study is being conducted to support a modification to the regulatory body approval of pulse oximeter probes reprocessed by Stryker Sustainability Solutions.

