#### 2.0 Scope

2.1	This procedure applies to the following Stryker Sustainability Solutions location(s):

	⊠ Tempe	□ Phoenix	□ Lakeland		☐ Chandler
--	---------	-----------	------------	--	------------

2.2 This study has been designed to include the subject devices listed in Table 1.

Study Device:			
OM	SKU	Minimum Quantity	Cycle Count
Masimo	4000 Adt (Adult)	10	4x
Masimo	4003 Neo (Adult & Neonate)	10	4x

Table 1: Subject devices

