#### **Procedure**

#### 7.0 **Summary**

Study Design:	T	
Study Type:	Interventional Non-significant Risk Lab Test	
Enrollment:	A typical study wi	ll include at least 10 subjects (up to 24 if needed to reach the 200
	necessary data po	oints to meet the ISO 80601-2-61:2019).
Allocation:	Non-randomized	
Intervention Model:	Parallel Assignmen	nt
Intervention Model Description:	Subjects will reclin	ne for the study. Reference sensors will be placed on each subject
	to evaluate the Sp	OO 2 accuracy and performance. Shield material may be used
	between any adjacent finger sensors to prevent optical crosstalk. A machine will	
	be used to induce motions of up to 20 mm during testing at a sine rate of 2Hz, 3Hz,	
	and 4Hz. A third motion moves the arm a random distance of up to 30mm at a	
	random speed up to 5Hz. Simultaneous data collection will be set up for devices	
	under test. The data from the test devices will be collected by the sponsor or	
	trained UCSF staff. Data will be collected for 1 second intervals data analysis. The	
	SpO 2 accuracy of the test devices will be evaluated over the oxygen saturation	
	range between 70-100%.	
Masking:	None (Open Label)	
Primary Purpose:	Device Validation	
Study Start Date:	May 27-28, 2023	
Arms and Interventions:		
Experimental: Masimo RD SET SpO2	2 Adhesive	Device: Stryker Sustainability Solutions Reprocessed Masimo
Sensors, Adult (4000 Adt), Adult & Neonate (4003		RD SET Pulse Oximetry Sensors

Neo)

Reference sensors from the reprocessed oximeter device will be placed on each subject to evaluate the SpO2 accuracy and performance.

An oximeter is a device used to transmit radiation at a known wavelength(s) through blood and to measure the blood oxygen saturation based on the amount of reflected or scattered radiation. Pulse oximetry monitoring is considered a standard physiological measurement and is used by clinicians in everyday situations to estimate arterial oxygen saturation. Because an arterial sample of blood is not required to make the measurement, the pulse oximeter can provide non-invasive real time information.

DF-CDS-109-11	UNCONTROLLED WHEN PRINTED
Rev. L	STRYKER CONFIDENTIAL - This document contains confidential and proprietary
Sustainability Document Template	information that is the property of Stryker Corporation. Neither this document nor the information herein may be reproduced, used or disclosed to any third party without the prior written consent of Stryker Corporation.

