#### **Primary Outcome Measures:**

 Accuracy of Sensor by Arms Calculation [ Time Frame: 1-5 hours ]

Percentage of SpO2 (oxygen saturation by pulse oximetry) measured by the Reprocessed Oximeter pulse oximetry sensors during motion conditions over the range of 70-100% SaO2 as compared to arterial blood samples assessed by CO-Oximetry.

The Accuracy root mean square (ARMS) between measured  $SpO_2$  and reference  $SaO_2$  (arterial oxygen saturation) must meet the 3% specification for each Stryker Sustainability Reprocessed pulse oximetry sensor style.

Accuracy will be determined by comparing the noninvasive blood oxygen saturation measurement of the pulse oximeter to that obtained from a blood sample and calculating the arithmetic root mean square error (Arms) value. In order to obtain the Arms value, the blood oxygen saturation measurement is subtracted from the pulse oximeter oxygen saturation measurement for a number of samples, the average of this difference is computed as the bias. The standard deviation of the differences is computed as the precision. The square root of the sum of the squares of bias and precision is computed as the Arms Error value.

For each range specified, SpO2 ACCURACY of the PULSE OXIMETER EQUIPMENT shall be stated in terms of the root-mean-square (rms) difference between measured values ( $SpO_{2i}$ ) and reference values ( $S_{Ri}$ ), as given by the following formula.

$$A_{\mathrm{rms}} = \sqrt{\frac{\displaystyle\sum_{i=1}^{n} \left(Sp\mathrm{O}_{2i} - S_{\mathrm{R}i}\right)^{2}}{n}}$$

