#### 10.0 Sample Size Designation

- 10.1 A typical study will include at least 10 subjects (up to 24 if needed to reach the 200 necessary data points to meet the ISO 80601-2-61:2019). Per FDA guidance, at least 2 or 15% of the subjects will have dark skin pigmentation. Skin pigmentation will be assessed using the Fitzpatrick scale by UCSF study personnel.
- 10.2 Each study subject will have two reprocessed sensors attached to their fingers. Two Reprocessed Masimo RD SET sensors should be placed on one side of the subject; however, sensors may be placed opposite sides. Digits selected should be two of the three middle fingers on each hand avoiding the thumb or pinky fingers as test sites.

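### Do 25.1.1, 16.2.4 and 10.2 need to repeat that each sensor style must meet 3% Arms, and to say which style each subject wears?

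*Combined protocol and SAP*

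**What the plan says.** The Primary Outcome Measures text in section 7.0 is the fullest statement of the criterion: Arms "must meet the 3% specification for each Stryker Sustainability Reprocessed pulse oximetry sensor style". Table 1, introduced by "This study has been designed to include the subject devices listed in Table 1", lists two styles, 4000 Adt and 4003 Neo, with a minimum of 10 sensors of each.

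Other places are shorter. Section 1.1 says that the "performance of the Stryker pulse oximetry sensors will meet a specification of +/-3" percent, for the sensors collectively. Section 25.1.1 asks for at least 200 data points and gives the limit as "Accuracy for the range of 70-100%, 3" percent Arms, without naming a style. Section 16.2.4 lists bias, precision and root mean square error, "all computed both overall and by several sub-ranges of desaturation". Section 16.2.2 asks for "Modified Bland-Altman plots for each instrument or instrument probe combination", and 16.2.3 for a regression of bias for each instrument.

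On layout, 10.2 says "Each study subject will have two reprocessed sensors attached to their fingers" and discusses hands and fingers, but not styles. Section 7.0 lists both styles in one experimental arm ("Sensors, Adult (4000 Adt), Adult & Neonate (4003" Neo), so the arms do not allocate them either. Section 15.1 gives the minimum as 200 data points and 10 subjects, stated together.

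**The concern.** Two things could go wrong if 25.1.1, 16.2.4 and 10.2 were read without the rest.

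First, a single Arms over both styles could be compared with 3%. A good style would then offset a poor one, and a style that fails the primary outcome could be reported as passing.

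Second, the number of subjects behind each style is not written down. Twenty sensors on 10 subjects can be one of each style on everyone, or two 4000 Adt on five people and two 4003 Neo on the other five. Both give the same number of pairs per style. If errors differ systematically between people, five subjects give a less precise Arms than ten, and no later analysis can recover the lost precision.

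**Working it through.** **Inputs.** Three saturation levels, four samples per plateau and two runs, with a stated 20-25 blood samples per subject (13.2); two sensors per subject (10.2); at least 10 subjects, up to 24 if needed to reach 200 points (10.1); 10 + 10 sensors (Table 1). The plan gives no error variance, expected Arms or within-subject correlation, so those are assumed below.

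**The plan's own count.** 3 × 4 × 2 = 24 samples per subject, inside 20-25. One sensor of a style on each of 10 subjects gives 10 × 20 = 200 pairs at the lower end, which is exactly the stated minimum.

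**Which reading do the counts support?** Pooled over both sensors, 10 subjects give 10 × 2 × 20 = 400 to 10 × 2 × 25 = 500 pairs. At least half could be lost before more subjects were needed to reach 200. Counted per style with one of each, the lower end is exactly 200, so a few lost readings (which 15.1 expects) would call for more subjects. The allowance of up to 24 therefore makes better sense per style. This is inference, but it agrees with the primary outcome text.

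**Subjects per style at N = 10.** If m subjects wear one of each and the rest wear matched pairs, split evenly, the count is 5 + m/2.
- m = 10: 10 subjects, 10 × 24 × 1 = 240 pairs per style, from 240 distinct blood samples.
- m = 0: 5 subjects, 5 × 24 × 2 = 240 pairs per style, from 5 × 24 = 120 distinct blood samples.
- Mixed layouts fall between. At N = 24 the two extremes are 24 and 12.

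**What five subjects would cost.** Simulation of one style (40,000 runs, 24 samples per subject) with normal errors of mean zero. The between-subject variance is share × Arms², and a subject wearing two of one style carries the same subject effect on both. Chance that observed Arms is at most 3% when true Arms is 3.3%:

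| Assumed between-subject share | 10 subjects × 24 | 5 subjects × 48 |
|---|---|---|
| 0 | 2.3% | 2.4% |
| 0.2 | 6.8% | 10.7% |
| 0.4 | 19.3% | 28.4% |

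At true Arms 3.0% and share 0.4, the standard deviation of observed Arms is 0.29 with 10 subjects and 0.38 with 5. For a style with true Arms 2.5% (5,000 runs, 20 samples per subject), the chance of a pass is 99.8% against 98.6% at share 0.2, and 97.5% against 93.4% at share 0.4.

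**The case for a change.** The strongest opposing case is that 25.1.1 is where the verdict is issued, so a condition missing there may not be applied. With equal numbers of pairs, pooled Arms is √((A² + B²)/2). A pooled value of 3.0% with one style at 2.0% lets the other reach √(18 − 4) = 3.74%. That arithmetic is right and needs no variance assumption. But it measures a reading that no section of the plan directs and that the primary outcome excludes with a mandatory per-style requirement. In 16.2.4, overall is set against saturation sub-ranges, so it most naturally means the whole 70-100% range and not both styles together. Sections 16.2.2 and 16.2.3 are already split by instrument or probe.

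The layout argument has more substance. Matched pairs are not ruled out in words. They would halve the subjects per style, and with the minimum of two dark-skinned subjects one style could be left with one or none. What stands is that the pairing is not written in 10.2. However, no section describes matched pairs, while 10 sensors of each style for 10 subjects wearing two each fits one of each directly. If the joint minimum of 200 points and 10 subjects follows the per-style outcome, five subjects per style would fail it. If it applies to the whole study, five would pass; 15.1 does not settle this. Section 12.1.2.1 has device use recorded for each subject, which should allow the layout to be checked.

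**Conclusion.** No change is needed. The per-style 3% criterion is explicit in the primary outcome, and 25.1.1 and 16.2.4 are shorter restatements that do not contradict it. An analyst working from the whole protocol would compute and judge Arms separately for 4000 Adt and 4003 Neo. The missing pairing in 10.2 is a detail that the plan's own numbers fill: one of each style per subject, which gives at least 10 subjects and about 200-250 pairs per style at N = 10.

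If that reading were wrong and matched pairs were used, the cost would be lower precision for each style. At an assumed true Arms of 3.3% the false-pass chance would be unchanged with no between-subject variance, about 4 percentage points higher at a share of 0.2 (10.7 − 6.8 = 3.9), and about 9 points higher at 0.4 (28.4 − 19.3 = 9.1). These sizes rest on the assumed Arms, the assumed shares and zero mean bias, none of which the plan supplies. The conclusion that the criterion applies per style rests on the text alone.
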